8.4. Examination of Subgroups

There are no specific plans to perform any subgroup analyses. However, subgroup analyses may be performed for categories of gender, age, race or other baseline characteristics as deemed clinically relevant and appropriate in further characterizing treatment effects.

8.5. Study Centers

The clinical study will be conducted under a common protocol for each of 4 investigational sites with the intention of pooling the data over all sites for analysis. Every effort will be made to promote consistency in study execution at each investigational site. Assuming there is not a high degree of imbalance in the number of participants from each site an initial analysis will be performed with Site as a blocking factor and accounting for site by treatment interaction. If there is no site by treatment interaction, the factor will be dropped from subsequent analyses. If site is deemed to significantly account for outcome variability, then subgroup analyses by site will be performed.

8.6. Data Review

Prior to unblinding of the study database, the data will be reviewed by the Clinical Project Manager. The investigational sites will be queried about any discrepancies or unclear data and, if necessary, these will be corrected in the database.

8.7. Derived Data

No variables will be derived.

8.8. Transformed Data

No data transformations are planned.

9. STUDY POPULATION

9.1. Participant Accountability

The number of participants in the study will be summarized by treatment and overall. The number of participants who were screened, the number who were randomized, the number in the SAF population, the number in the ITT population, and the number in the PP population will be summarized by treatment and overall.

9.2. **Protocol Deviations**

Participant data will be reviewed for major protocol violations by a qualified clinical reviewer prior to database lock and unblinding. Participants with any major protocol violations will be excluded from the Per Protocol Population. The major protocol deviation is defined as:

- Outside the age window
- Deleterious concomitant medications
- Compliance < 80%
- Tattoo outside the specified location

All other protocol deviations will be considered as minor. The major protocol deviations and the descriptions will be listed by participants.

9.3. Treatment Compliance

A review of treatment compliance will begin with a telephone interview at Visit 3 (approximately 7 days after baseline). Participants are expected to use the use the caps for 10 minutes every day. The percent compliance will be based on the actual number of days used divided by the expected number of days available to use. For example, if a participant uses the cap 50 times over the course of 56 days, compliance will be 89.3%. The number of days of participation and percent compliance by will be summarized by treatment group.

9.4. Other Descriptions of Study Population

Demographics data will be summarized by treatment group and overall. Demographics will include age, gender, baseline height and baseline weight.

Baseline characteristics will be summarized by treatment group and overall. Baseline characteristics include hair count, responses to Hair Specific Skindex-29 questionnaire, and blinded reviewer Physician's Global Assessments from photographs.

Medical history, physical exam and vital signs findings will be summarized by treatment group and overall.

Prior medications are any medications taken and stopped prior to initiating treatment with a Revain cap. Prior medications will be collected as part of the medication history. These will be coded to Anatomical Therapeutic Classification (ATC) and by the preferred medication

names using WHO-Drug dictionary (WHODrug Mar-15) Incidence of participants having taken prior medications will be summarized by treatment group and overall.

Concomitant medications are defined as any medication that started prior to treatment initiation and is ongoing, or any medication that starts after the initiation of treatment. These will be handled as part of the safety assessments.

10. EFFICACY ANALYSES

10.1. Primary Endpoint

The primary efficacy endpoint is the change from baseline in hair count, over a pre-specified 1 cm² area of scalp after 16 weeks of treatment (CFB_HC16).

As specified in Section 9.2, each active cap will be compared to the same Sham treatment using 1 degree of freedom contrasts in an analysis of covariance (ANCOVA). Analyses will be adjusted for multiple comparisons using Dunnett's correction. An example of SAS code to be used for the primary analysis is as follows:

PROC MIXED; CLASS SITE ARM; MODEL CFB_HC16 = SITE ARM SITE*ARM <covariates>; LSMEANS ARM /ADJUST=DUNNETT DIFF=CONTROL('SHAM'); RUN;

If the SITE*ARM interaction is not significant (p>0.05), this interaction will be dropped from the subsequent model. SITE will remain in the model if it significantly attributes to variability of the outcome. All subsequent analyses of secondary endpoints will retain the same factors and covariates as the primary outcome analysis.

10.2. Secondary Analyses

Secondary efficacy endpoints will be analysed as follows:

Change from Baseline Hair Count: the change from baseline hair count at 8 (CFB_HC08) and 26 (CFB_HC26) weeks will be analyzed in the same manner as the primary endpoint.

Rate of Change in Hair Growth: The rate of change in hair growth at 8, 16 and 26 weeks will be analyzed in the same manner as the primary endpoint.

Independent Physician's Global Assessment (iPGA): The percentage of participants with each score will be summarized by treatment group and by week. The active cap groups will be compared to the Sham group using Cochran-Mantel Haenszel (CMH) chi-squared method for detecting shifts in distribution of answers. The modified RIDIT scores will be used to take into account the ordered nature of the categorical responses. An example of SAS code for this analysis is as follows:

```
IF ARM IN ('SHAM', 'CAP101');
PROC FREQ;
```

TABLE ARM*(iPGA08 iPGA16 iPGA26) /CMH SCORE=MODRIDIT; RUN;

Site Physician's Global Assessment (sPGA): The site investigator will assess over hair growth using the PGA scores at weeks 8, 16 and 26. These outcomes will be summarized and analysed in the same manner as the iPGA, above.

Subjective Scalp Hair Growth Score (SHG): The percentage of participants with each score in for each question will be summarized by week and by treatment group. The active cap groups will be compared to the Sham group using Cochran-Mantel Haenszel (CMH) chi-squared method for detecting shifts in distribution of answers. The modified RIDIT scores will be used to take into account the ordered nature of the categorical responses. An example of SAS code for this analysis is as follows:

```
IF ARM IN ('SHAM', 'CAP101');
PROC FREQ;
TABLE ARM*(SHG1 SHG2 SHG3 SHG4 SHG5A SHG5B SHG5C)
/CMH SCORE=MODRIDIT;
RUN;
```

Hair Specific Skindex-29 Quality of Life Questionnaire (HSSQOL): The sum of scores for overall will be summarized by treatment group for each visit. These outcomes will be summarized and analysed in the same manner as the SHG above.

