3.4.3 Randomization of Treatment Device

All participants will be randomized to one of four study arms. The randomization will be a block design, stratified across the sites and maintained by the local Study Sponsor. Each site will be blinded to the randomization code and will only receive a pre-assigned code to use for each participant at time of enrollment. The code will be pre-assigned to one of the four caps below:

Study Arm 1: Active REVIAN Cap 101Study Arm 2: Active REVIAN Cap 102Study Arm 3: Active REVIAN Cap 103Study Arm 4: Non-Active REVIAN (SHAM) Cap 100

3.4.4 Week 1 Phone Call – (7±3 Days), Visit 3

- Concomitant medication usage
- Adverse Events
- Compliance Follow-up

3.4.5 Week 8 Follow-Up Visit – (56±5 Days), Visit 4

- Subjective Scalp Hair Growth (SSHG) Score
- Physician's Global Assessment (PGA) Score
- Hair Specific Skindex-29 Quality of Life Questionnaire
- Global Photography Image of Two Views (superior and vertex scalp)
- Shave and Tattoo Scalp
- Hair Count Macrophotography (1cm² Area)
- Concomitant medication usage
- Adverse Events
- Compliance Follow-up

3.4.6 Week 16 Follow-Up Visit – (112±10 Days), Visit 5

- Subjective Scalp Hair Growth (SSHG) Score
- Physician's Global Assessment (PGA) Score
- Hair Specific Skindex-29 Quality of Life Score Questionnaire
- Global Photography Image of Two Views (superior and vertex scalp)
- Shave and Tattoo Scalp
- Hair Count Macrophotography (1cm² Area)
- Concomitant medication usage
- Adverse Events
- Compliance Follow up

3.4.7 Week 26 Follow-Up Visit – (182±10 Days), Visit 6

- Physical Exam (including vital signs)
- Subjective Scalp Hair Growth (SSHG) Score:
- Physician's Global Assessment (PGA) Score:
- Hair Specific Skindex-29 Quality of Life Score Questionnaire
- Global Photography Image of Two Views (superior and vertex scalp)
- Shave and Tattoo Scalp
- Hair Count Macrophotography (1cm² Area)
- Concomitant medication usage
- Adverse Events
- Compliance Follow up
- Exit/Termination Form

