APPENDIX B: HAIR SPECIFIC SKINDEX-29 QUALITY OF LIFE QUESTIONNAIRE

Scoring:

Sx: Symptom (7-35), Em: Emotion (10-50), Fx: Function (12-60) Total Scoring = (29-145)

APPENDIX C: Physician's Global Assessment (PGA) Scoring and Subjective Scalp Hair Growth (SSHG) Evaluations

A Canfield stereotactic positioning device will be used for obtaining global photographs where the participant's chin and forehead are fixed, and on which a given camera and flash device are mounted to standardize the view, magnification and lighting at consecutive study visits. Participants will be asked to keep the same hair style and colour and the coordinators attempt to duplicate baseline hair parting and combing in subsequent follow-up visits. Two standard views (superior and vertex) will be taken at baseline, 8-, 16, and 26-weeks (Figure 5). The digital images will be graded. Paired baseline and post-treatment photographs will be evaluated by each site study doctor (at the Week 8, 16 & 26 follow up visits) in order to provide a physician global assessment (*sPGA*) score.

In addition, the photographs will then be independently reviewed by two blinded evaluators, to evaluate the independent physician's global assessment (iPGA)

The PGA score used is the standardized 7-point rating scale (-3 = greatly decreased, -2 = moderately decreased, -1 = slightly decreased, 0 = no change, +1 = slightly increased, +2 = moderately increased, +3 = greatly increased increased).

Figure 5. Global Photography, demonstrating fixation of the participant on a brow and chin rest with the camera mounted on a rotating arm.

Participants will be asked to assess subjective scalp hair growth (SSHG). They will be provided with the following questionnaire at each follow up visit (8, 16 and 26 weeks after baseline).

Subjective Scalp Hair Growth (SSHG)

1. Since the start of the study, I can see my bald spot getting smaller

Strongly Agree	Agree	No opinion either way	Disagree	Strongly Disagree
1	2	3	4	5

2. Because of the treatment I have received since the start of the study, the appearance of my hair is:

A lot better	Somewhat better	A little better	Same	A little worse	Somewhat worse	A lot worse
1	2	3	4	5	6	7

3. Ever since the start of the study, how would you describe the growth of your hair?

Greatly increased	Moderately increased	Slightly increased	No change	Slightly decreased	Moderately decreased	Greatly decreased
1	2	3	4	5	6	7

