3. STUDY DESIGN

This study is designed as a prospective, randomized, controlled, double-blind, four-arm study. Up to 3 clinical sites will enroll up to 200 participants over an approximate 6-month duration. Eligible participants with AGA meeting all inclusion and exclusion criteria will be enrolled and randomized to one of four study arms in a 1:1:1:1 ratio:

- Arm 1: Active *REVIAN* 101 (___mW/cm² of 625 nm and 660 nm)
- Arm 2: Active *REVIAN* 102 (____mW/cm² of 425 nm)
- Arm 3: Active *REVIAN* 103 (____mW/cm² of 425 nm + ___mW/cm2 of 625 nm and 660 nm)
- Arm 4: Non-Active *REVIAN* Cap 100 (SHAM)

Male and female participants will be randomized from separate randomization schedules to ensure balance among treatment arms in each gender.

All data except for Global Assessment Photography and Macrophotography will be captured in an electronic clinical report form (eCRF). Global Assessment Photography and Macrophotography data will be imported from external vendor. Demographic, baseline characteristics, efficacy and safety data will be collected at regularly scheduled visits according to the planned schedule of procedures (Table 1).

Screening procedures will be performed at Visit 1.

Participants who are eligible to enroll will return within 7 days for Visit 2 to obtain baseline data and to be randomized to one of the treatment arms. The first treatment will be performed in the clinic on Visit 2.

Visit 3 will occur approximately 7 days later via telephone interviews to assess treatment compliance, to report use of concomitant medications and to report any adverse events.

Visits 4 and 5 will occur approximately 8 and 16 weeks, respectively, after Visit 1. Participants will return to the investigation centers for efficacy assessments and questionnaires.

The final visit (Visit 6) will occur approximately 10 weeks after Visit 5. Participants will undergo a final assessment of efficacy and safety at Visit 6. Participants will return the caps at Visit 6. If there are no adverse events requiring follow-up, participants will not need to return for any follow up assessments.

Any participant who competes the Week 16 efficacy assessments (at Visit 5) will be considered a completer.

Visit 1	Visit 2	Visit 3	Visit 4	Visit 5	Visit 6
Screening (Day -7)	Baseline (Day 0)	Phone Call (7 ±3 Days)	Week 8 ^{1,2} (56 ±5 Days)	Week 16 ^{1,2} (112 ±10 Days)	Week 26 ^{1,2} (182 ±10 Days)
X	Х				
X					
Х					
X					
X	Х				
X	Х				
	Х				Х
	Х				
	Х		Х3	X ³	X ³
	Х		Х	Х	Х

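### SAP 10.2 codes the CMH tests for iPGA and SSHG (and by reference sPGA and HSSQOL) without the randomisation strata: each comparison stays valid but loses power to the extent that site and sex predict the score

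*Combined protocol and SAP*

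**What the plan says.** Protocol 3.4.3 sets one stratum: "The randomization will be a block design, stratified across the sites and maintained by the local Study Sponsor". SAP 3 sets a second: "Male and female participants will be randomized from separate randomization schedules to ensure balance among treatment arms in each gender". It also states that participants are "randomized to one of four study arms in a 1:1:1:1 ratio". Block size is not given.

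In SAP 10.2, after the data are restricted to sham and one active cap, the iPGA code reads "TABLE ARM*(iPGA08 iPGA16 iPGA26) /CMH SCORE=MODRIDIT; RUN".

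For the SSHG items it reads "TABLE ARM*(SHG1 SHG2 SHG3 SHG4 SHG5A SHG5B SHG5C", with the same options.

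The sPGA is to be analysed like the iPGA, and the HSSQOL total like the SSHG. Both code blocks are labelled as examples, but they are the only specification of how the CMH tests are built.

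SAP 10.1 states: "All subsequent analyses of secondary endpoints will retain the same factors and covariates as the primary outcome analysis". The sentence before it makes site conditional: "SITE will remain in the model if it significantly attributes to variability of the outcome". SAP 8.3 keeps a covariate, gender among them, only at p<0.10.

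On who scores the sPGA, protocol Appendix C says: "Paired baseline and post-treatment photographs will be evaluated by each site study doctor". Protocol 3.3 allows the Principal Investigator, designated Sub-Investigators, or both to act as blinded evaluators.

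**The concern.** Blocked randomisation within site and sex keeps the arms balanced on both, so differences between strata largely cancel out of the comparison between arms. A test on the pooled table does not use this. Its variance still contains the between-stratum part, so the statistic is scaled by too large a standard error. The consequence is a conservative comparison with less power, not a false-positive problem.

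There is also a drafting conflict. One programmer could follow the code and leave site and sex out. Another could follow SAP 10.1 and carry over whatever the primary model retained. They could report different p-values for the same endpoint.

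Following SAP 10.1 would not reliably solve this, because the screen is applied to the wrong outcome. Hair-count macrophotography data come from an external vendor (SAP 3), while the sPGA is scored at the site. Site may matter little for hair count and a good deal for the sPGA, whose raters are nested within site. That makes the sPGA plausibly the most exposed of the four endpoints.

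**Working it through.** **The plan's own figure.** The only power statement (protocol 5.2, SAP 5) is for hair count: difference 15, SD 20, two-sided 5%, 90% power. Then n = 2 × (1.960 + 1.282)² × 20² / 15² = 37.4, so 38 per arm; the t-test version gives 38.3, so 39. The stated 40 reproduces, with power at 40 of 0.918 (normal) or 0.912 (t). No power or effect size is given for iPGA, sPGA, SSHG or HSSQOL.

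**Inputs.** From the documents: strata of site and sex, taken here as crossed; 1:1:1:1 allocation; 200 participants; about 60% men and 40% women; 10% dropout; 3 or 4 sites (SAP 3 and protocol 5.2 say 3, while SAP 8.5 and the protocol synopsis say 4). Assumed: R², the share of score variance explained by the strata; block size 8; a latent shift of 0.6 within-stratum SD.

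**Analytic check.** With balanced strata, the unstratified statistic has null variance 1 − R² instead of 1. Its true size at nominal 0.05 is 2 × [1 − Φ(1.960 / √(1 − R²))]. If the stratified test has 80% power, its mean is 1.960 + 0.842 = 2.802, and the unstratified power is Φ(2.802 − 1.960 / √(1 − R²)). At R² = 0.20: 1.960 / 0.894 = 2.191, so size = 2 × [1 − Φ(2.191)] = 0.028 and power = Φ(0.610) = 72.9%.

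**Simulation.** The coded modified-ridit CMH test was compared with the same test stratified by site × sex (the van Elteren test), on a 7-point score with 2,500 runs per cell. In the simulation R² is on the latent scale. Near 73% power the Monte Carlo standard error is √(0.73 × 0.27 / 2500) = 0.9 points.

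| R² (assumed) | True size, unstratified | Unstratified power where stratified = 80% | Simulated power, 4 sites: unstratified vs stratified | Simulated power, 3 sites: unstratified vs stratified |
|---|---|---|---|---|
| 0 | 0.050 | 80.0% | 74.6% vs 73.6% | 77.0% vs 75.0% |
| 0.05 | 0.044 | 78.5% | 73.6% vs 73.8% | 75.1% vs 75.8% |
| 0.10 | 0.039 | 76.9% | 71.5% vs 73.0% | 73.1% vs 75.5% |
| 0.20 | 0.028 | 72.9% | 67.7% vs 72.5% | 68.0% vs 74.7% |
| 0.30 | 0.019 | 67.7% | 60.6% vs 71.8% | 62.1% vs 73.9% |

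**Interaction with multiplicity.** SAP 8.2 applies the primary testing process, which includes Dunnett's correction, to the secondary outcomes; the CMH code has no adjustment. Three tests against one sham at 1.96 have a family-wise error of 0.125 at R² = 0. Without strata this becomes 0.099, 0.074 and 0.051 at R² = 0.10, 0.20 and 0.30. With the Dunnett critical value of about 2.35 in place, the cost of omitting strata is slightly larger. An 80% stratified power becomes Φ(2.348 + 0.842 − 2.348 / √(1 − R²)) = 71.4% at R² = 0.20 and 64.9% at 0.30.

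**The case against.** The code is offered as an example, and SAP 10.1 already says that the primary factors carry over. This stands in part. If site survives in the hair-count model, the text asks for it in the secondaries too. But retention depends on significance for another outcome, and nothing shows how a retained factor enters a CMH test.

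The harm is assumed, because the documents give no site or rater variance. This stands in full. At R² of 0.10 or less the loss lies between nothing and about 3 points over the analytic and simulated figures, and at R² = 0 the stratified test is 1 to 2 points worse in simulation.

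The rater argument has limits. A reader might infer that site and rater are the same thing for the sPGA, but protocol 3.3 lets Sub-Investigators rate, so a site may have several raters. A reader might also carry the argument over to the other endpoints. The iPGA, however, is read by two independent reviewers, with the PI's score superseding only on disagreement (SAP 8), and participants complete the SSHG and HSSQOL themselves. Those endpoints belong in the fix because the trial randomises by site and sex, not because of rater leniency.

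Site × sex strata can be thin. With four equal sites, a pairwise comparison of 50 + 50 has about 40 women, or 40 / 4 / 2 = 5 per arm per site. Protocol 2.5 lets one site enrol 100. The other three would then average 100 / 3 / 4 = 8.3 participants per arm, of whom about 3 would be women. This stands, and calls for a fallback rule fixed in advance.

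**Conclusion.** The concern holds as a conditional loss of efficiency together with a contradiction between SAP 10.1 and 10.2. Each coded comparison is valid. If site and sex explain 20% to 30% of score variance, the loss is about 5 to 12 points of power; if they explain little, it is negligible. These sizes rest on assumed R², near-balanced strata and a test at 5% per comparison.

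A reader might infer that the secondary p-values are too large overall. The documents do not support that. It is true only of the missing strata, within one comparison. The same code omits the multiplicity adjustment that SAP 8.2 calls for, which pushes the other way. Across the three comparisons the net result is anti-conservative until R² reaches about 0.30. The two defects are separate, and neither excuses the other.

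The endpoints are secondary and validity is intact, but the change is cheap and the contradiction needs resolving in any case, so it should be made.

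**What to change.** - In SAP 10.2, replace the table request with `TABLES SITE*SEX*ARM*(score) / CMH SCORES=MODRIDIT;` and name the row-mean-scores statistic. Apply it to iPGA, sPGA, every SSHG item and HSSQOL.
- State that both strata are used whether or not site or sex is significant in the hair-count model.
- Before unblinding, fix a blinded rule for falling back to SITE alone, for example one based on stratum counts pooled over arms.
- Amend the last sentence of SAP 10.1 so that it agrees with SAP 10.2.
- In the same revision, state the multiplicity adjustment for the CMH tests against the shared sham.

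The cost is a changed line in each code block and a few SAP sentences, with no new data. The downside is about 1 to 2 points of power if the strata turn out not to be prognostic.

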2.4 Study Endpoints

2.4.1 Primary Efficacy Endpoint:

The primary efficacy endpoint of this study is mean change in hair count from baseline to 16 weeks following the initial application at baseline.

2.4.2 Secondary Efficacy Endpoints:

Secondary efficacy endpoints will be determined using the following outcome measurement tools to evaluate changes at each follow up visit compared to baseline:

- 1. *Change from Baseline Hair Count*: Like the primary endpoint, change from baseline hair count, will also be assessed at 8 and 26 weeks.
- 2. Rate of Change in Hair Growth: The rate of change in hair growth at 8, 16, and 26 weeks will be calculated as a ratio of change from baseline to baseline.
- 3. Independent Physician's Global Assessment (iPGA): An independent reviewer will assess over hair growth over baseline from photographs, using PGA scores at weeks 8, 16 and 26. The PGA score hair growth as: -3=greatly decreased, -2=moderately decreased, -1=slightly decreased, 0=no change, 1=slightly increased, 2=moderately increased and 3=greatly increased
- 4. *Site Physician's Global Assessment (sPGA)*: The site investigator will assess over hair growth using the PGA scores at weeks 8, 16, and 26.

In addition, the percentage of participants who achieve success as defined by a PGA ≥ 2 will be summarized by treatment and by weeks.

- 5. *Subjective Scalp Hair Growth Score (SSHG): SSHG* will be administered beginning at 8 weeks and then at 16 and 26 weeks.
- 6. *Hair Specific Skindex-29 Quality of Life Score Questionnaire (HSSQOL)*: The hair specific Skindex-29 QOL questionnaire will be administered at baseline, 8, 16, and 26 weeks.
- 7. Overall Treatment Success (OTS): Overall treatment success will be defined as the number of participants who achieve ≥50% reduction in overall QOL scores, plus reported SSHG ≥2 on every question.

2.4.3 Primary Safety Endpoint(s):

At each follow-up visit, participants will be interviewed to determine if any adverse events (AEs) were experienced since the previous follow-up visit. If deemed necessary, a physical assessment may be performed for any participant experiencing a serious adverse event or as required by the Principal Investigator. The primary safety outcomes will be determined by evaluating by the type, frequency, severity, and relatedness of adverse events through the 26-week period for all participants.

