- 2) Because of the treatment, I have received since the starts if the study, the appearance of my hair is: (1="a lot better" to 5="a lot worse")
- 3) Ever since the start of the study, how would you describe the growth of your hair? (1="greatly increased" to 7="Greatly decreased")
- 4) Ever since the start of the study, how effective do you think the treatment has been in slowing down your hair loss? (1="Very effective" to 4="Not effective at all")
- 5) Compared to the beginning of the study, which statement best describes your satisfaction with your appearance of:
 - a. The hairline in front of your head? (1="very satisfied" to 5="very dissatisfied")
 - b. The hair on top of your head? (1="very satisfied" to 5="very dissatisfied")
 - c. Your hair overall? (1="very satisfied" to 5="very dissatisfied")

SHG will be administered at 8 weeks, 16 weeks and 26 weeks

Hair Specific Skindex-29 Quality of Life Questionnaire (HSSQOL): The hair specific skindex-29 QOL questionnaire is a 29-item questionnaire with 3 domains: 7 questions for symptoms domain, 10 questions for emotion domain and 12 questions for function domain. Participants score each question on a scale from 1 (never) to 5 (all the time). Total scores will be summed at Week 8, 16 and 26. HSSQOL will be administered at baseline, 8, 16 and 26 weeks.

Secondary Safety Endpoint: The secondary safety outcome will be determined by evaluating by the type, frequency, severity, and relatedness of adverse events through the 26-week period for all participants.

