8.1. Missing and Imputed Data

Every effort will be undertaken to fulfill all the requirements of the protocol concerning the collection of data. If participants refuse to return for data collection, but agree to continue in the study, questionnaire data and safety data will be collected over the telephone or at a home visit, if necessary.

The primary analysis will be performed on the ITT group. Those participants who withdraw or who are lost to follow up (LTFU) after enrollment will be included in the primary analysis using a last observation carried forward (LOCF) approach where the outcome at the most recent visit will be carried forward to all subsequent missing assessment times. Since all postbaseline efficacy assessments are first assessed at approximately Week 8, participants without an 8-week visit will have their baseline observation carried forward (BOCF) for the primary and secondary efficacy analyses. Analyses will also be performed on all available data with no imputations.

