8.2. Hypothesis Testing

The treatment consists of 3 active caps and one Sham cap. Each active cap group will be compared to the same Sham group using 1 degree of freedom contrasts in general linear models analysis of covariance (ANCOVA). Comparisons will be adjusted for multiple comparisons to the same Sham group using Dunnett's correction.

The primary outcome is the change from baseline in hair count after 16 weeks of treatment with a cap. The null hypothesis is there is no difference in outcome between an active cap compared to a Sham cap, while the alternative hypothesis is there is a difference outcome between active compared Sham cap:

 H_{null} : $D_{active} = D_{Sham}$

 $H_{alternative} \text{: } D_{active} \neq D_{Sham}$

The null hypothesis will be rejected in favor of the alternative hypothesis for each active cap if the Dunnett's corrected p-value for the contrast ≤ 0.05 . Treatment superiority will be

demonstrated if the significant difference is in favor of the active cap (e.g., greater increase in hair count for the active cap. No comparisons between active caps will be performed.

Secondary outcomes will the same hypotheses testing process as the primary outcome, but with statistical methods appropriate for the type of endpoints to be tested. For example, continuous outcomes will be analysed by parametric methods, such as ANCOVA, while categorical outcomes will be analysed by non-parametric methods, such as Cochran-Mantel-Haenszel (CMH) test. Details of analyses by outcomes are provided in Section 10.

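### SAP 10.2 tests the Skindex-29 (HSSQOL) visit total without its baseline score, which is valid but gives up precision on a secondary endpoint

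*Combined protocol and SAP*

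**What the plan says.** SAP 10.2 defines the HSSQOL variable as the visit total: "The sum of scores for overall will be summarized by treatment group for each visit". It then sends that total to the method used for the subjective hair growth questionnaire (SHG): "These outcomes will be summarized and analysed in the same manner as the SHG above". The SHG method cuts the data to sham plus one cap and runs a CMH test with modified ridit scores. The example code has no strata and no baseline term.

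Other passages bear on the choice:

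- SAP 8 confirms that a baseline exists: "HSSQOL will be administered at baseline, 8, 16 and 26 weeks". SHG and the physician's global assessments have none, as the notes to both visit schedules say.
- Protocol 2.4.2 introduces all the secondary endpoints as tools "to evaluate changes at each follow up visit compared to baseline".
- SAP 8.1 already uses the baseline score as an outcome for some participants: "participants without an 8-week visit will have their baseline observation carried forward (BOCF) for the primary and secondary efficacy analyses".
- SAP 8.2 gives a general illustration, "For example, continuous outcomes will be analysed by parametric methods, such as ANCOVA", and leaves the detail for each outcome to Section 10.
- On multiplicity, SAP 8.2 states that "Comparisons will be adjusted for multiple comparisons to the same Sham group", by Dunnett's method, and extends this to the secondaries: "Secondary outcomes will the same hypotheses testing process as the primary outcome".

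**The concern.** A test built for questionnaires with no baseline has been borrowed for one that has a baseline. Where baseline and follow-up scores are correlated, part of the spread in the visit totals is predictable from baseline. Leaving baseline out puts that part into the error term. It also leaves the comparison open to chance baseline differences between arms, and it does not directly address change, which is what protocol 2.4.2 describes.

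At stake is the chance of detecting a real quality-of-life effect with data the trial collects anyway. The primary hair-count analysis is untouched.

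**Working it through.** **Could baseline HSSQOL enter by another route?** SAP 9.4 lists the Skindex-29 responses as a baseline characteristic, and the covariate list in SAP 8.3 is open-ended, so baseline HSSQOL could enter the p<0.10 screen. SAP 10.1, however, carries to the secondaries the covariates kept for hair count. Baseline HSSQOL would then survive only if it happened to predict hair count. Even so, the CMH code has no place for a continuous covariate. Neither route reliably brings it in.

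**Inputs from the documents.** Four arms at 1:1:1:1 (SAP 3), at least 40 evaluable per arm and up to 50 accrued (SAP 5), and Dunnett correction against sham (SAP 8.2).

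**The plan's own figure.** SAP 5 assumes a difference of 15, SD 20, two-sided 5% alpha and 90% power. Then n = 2(1.960 + 1.282)² × 20²/15² = 37.4, so 38 per arm. The exact t-test gives 39, and power at 40 is 91-92%. The stated 40 is reproduced. It refers to hair count. The documents give no power or SD for HSSQOL.

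**Assumptions.** A 0.5 SD effect in one cap, and baseline-to-visit correlation r = 0.3, 0.5 or 0.7.

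**Thresholds.** For three contrasts sharing one sham (correlation 0.5), the Dunnett critical value is 2.349 on the z scale (p = 0.0188), 2.372 for the four-arm t contrast at 40 per arm, and 2.367 at 50 per arm. Both methods are held to this level.

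**Arithmetic at 40 per arm.** Adjusting for baseline multiplies the residual variance by 1 − r², which is 0.91, 0.75 or 0.51. The standardised contrast is 0.5 × √(40/2) / √(1 − r²) = 2.236 / √(1 − r²):

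- r = 0.3: 2.344; power Φ(2.344 − 2.372) ≈ 49%
- r = 0.5: 2.582; power Φ(2.582 − 2.372) ≈ 58%
- r = 0.7: 3.131; power Φ(3.131 − 2.372) ≈ 78%

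For the ridit test, with the usual large-sample efficiency of 0.955, 2.236 × √0.955 = 2.185 and Φ(2.185 − 2.349) ≈ 43%, whatever r is.

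**Simulation.** 20,000 four-arm trials per cell, with bivariate normal scores. A separate run of 12,000 trials per cell agreed to about 1 point. Each pair is ridit / baseline-adjusted ANCOVA, in per cent.

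| Setting | r = 0.3 | r = 0.5 | r = 0.7 |
|---|---|---|---|
| 40 per arm, no imputation | 41.8 / 49.1 | 41.2 / 57.6 | 41.0 / 76.9 |
| 50 per arm, baseline carried forward for 10% | 41.7 / 51.3 | 41.8 / 61.9 | 42.2 / 82.1 |
| 50 per arm, baseline carried forward for 20% (upper bound) | 32.3 / 43.1 | 32.9 / 54.6 | 32.6 / 75.3 |

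The first row is the main result, with gains of about 7, 16 and 36 points. Both carry-forward rows treat every dropout as lost before week 8. SAP 8.1 carries baseline forward only for those without a week-8 visit, and later dropouts carry their last visit. The 20% row (gains of about 11, 22 and 43 points) is therefore an upper bound. If dropouts instead carry a week-8 value with the same effect and r, the gain at 50 per arm is about 8, 19 and 34 points.

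**Entry cut-off.** Eligibility requires an HSSQOL total of at least 45, which narrows the baseline range. With an assumed position for that cut-off, the gain at 40 per arm falls to about 6, 11 and 25 points.

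**Error check.** With no effect, 50 per arm and 10% carried forward, one-sided rejection by the ANCOVA is 0.0087-0.0098 against a nominal 0.0094.

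**The case against.** The strongest reply is that the choice in 10.2 is legitimate. A rank-type test on a bounded sum of five-point items is accepted practice, randomisation makes it valid, and the plan claims no power for HSSQOL. The wording in protocol 2.4.2 introduces seven endpoints at once, and the HSSQOL item itself says only when the questionnaire is given. The power gain rests on an assumed effect, an assumed r and normal scores. All of this stands. It limits the point to lost precision on a secondary endpoint, with a size that depends on r. It does not explain why a baseline already in hand should be left out.

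Two stronger readings are tempting, and the documents do not support them.

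A reader might infer that 10.2 breaks 8.2 by not using ANCOVA. In 8.2, ANCOVA is offered as an example and the detail is left to Section 10, so this is at most a loose fit.

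A reader might also infer that the CMH-tested secondaries have no multiplicity control, since the example code returns one raw p-value per cap. Three such tests at 0.05 would give a family-wise error of about 12.5% for one outcome at one visit. But 8.2 sets the Dunnett correction and gives the secondaries the same testing process, and the code in 10.2 is presented only as an example. The 12.5% would come from departing from the plan, not from following it. Nor does protocol 5.2 help this reading: its sentence leaving multiplicity detail to the SAP closes the paragraph on the primary analysis. What is missing is only the mechanics for a CMH p-value.

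**Conclusion.** The point holds as an inefficiency. The HSSQOL test in 10.2 is valid but ignores a baseline score that the trial collects and that protocol 2.4.2 implies should be used. At 40 per arm and a Dunnett-level threshold, power is about 41%, against about 49, 58 or 77% with baseline adjustment at r = 0.3, 0.5 or 0.7. Allowing for an assumed entry cut-off, the gain is about 6, 11 or 25 points. These figures rest on an assumed 0.5 SD effect, the assumed range of r and normal scores. The direction does not depend on the exact values as long as r is clearly above zero. The change is worth making because it costs little. It bears only on secondary claims.

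**What to change.** In SAP 10.2, analyse the HSSQOL visit total (or its change from baseline) by ANCOVA. Name baseline HSSQOL as a fixed covariate, exempt from the p<0.10 screen, and add the factors retained in the primary model. Use Dunnett contrasts against sham, as 8.2 requires. Keep the ridit test as a sensitivity analysis.

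As a minor clarification, 10.2 could also say how the correction in 8.2 is applied to the three cap-versus-sham CMH p-values at each visit for the independent and site physician assessments and for each SHG item, for example a threshold of p ≤ 0.0188, or Holm's procedure.

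The cost is SAP wording and a small change to the code, made before unblinding. No new data are needed. The ANCOVA needs roughly normal residuals on a bounded sum, so residuals should be checked; the ridit result serves as the safeguard.
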